#### 1. Background and Purpose

Monocyte migration plays a key role in the pathogenesis of Rheumatoid arthritis (RA) since the number of monocyte derived macrophages is higher in RA synovial tissue compared to normal joints and is well correlated with radiological damage, joint pain and inflammation. However, the signaling pathway(s) responsible for enhanced recruitment of monocytes into the RA synovial joint space is unknown. To address this important issue, we performed microarray studies to identify differentially regulated genes in RA synovial fluid macrophages and identified IL-7 Receptor (IL-7R) as one of the most highly upregulated genes in RA synovial fluid macrophages. Our preliminary data shows that IL-7R expression is elevated 45 fold in RA synovial fluid and 10 fold in RA peripheral blood (PB) in vitro differentiated macrophages compared to normal PB macrophages by real-time RT-PCR and/or FACS analysis. Consistently, in RA synovial tissue, IL-7R is also elevated on macrophages in the lining and sublining compared to normal synovial tissue. We found that expression of IL-7R in RA PB monocytes and macrophages is modulated by TNF- $\alpha$  Interestingly, concentrations of IL-7R have a strong correlation with disease activity score as determined by 28 joint count (DAS28) and TNF-α levels in RA monocytes. Moreover, our preliminary data documents that IL-7 is secreted from TNF-a treated RA macrophages and can attract IL-7R+ monocytes from the circulation to the RA joint at concentrations of IL-7 detected in RA synovial fluid.

Based on our results we hypothesize that RA patients with a TNF- $\alpha$  driven active disease have elevated expression of IL-7/IL-7R and thereby response to anti-TNF- $\alpha$  therapy reduces IL-7-mediated monocyte migration and the number of IL-7R+macrophages in the RA joint. To test our hypotheses, in aim 1 we will examine whether expression of IL-7 or IL-7R in RA PB cells correlates with RA disease severity and response to anti-TNF- $\alpha$  treatment (Fig. 1). To date the contribution of IL-7 and IL-7R to RA pathogenesis and its role as a TNF- $\alpha$  responsive gene has not been described.

IL-7R is the top gene identified in synovial fluid macrophages and its expression in monocytes ( $R^2=0.56$  and  $p=8.4x10^{-5}$ ) and macrophages ( $R^2=0.56$  and  $p=2.4x10^{-6}$ ) strongly correlates with RA disease activity suggesting that IL-7R may be a predictor for disease severity. Hence in this proposal, novel translational studies will be performed in order to determine whether IL-7R and IL-7 are RA signature genes for disease activity and if these genes are markedly reduced in anti-TNF- $\alpha$  therapy responders compared to nonresponders.

**Figure 1.** Specific aim is proposed to elucidate the significance of IL-7/IL-7R expression in peripheral blood cells to RA disease activity and response to anti-TNF- $\alpha$  treatment.

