#### 2. Protocol Methodology

**Detection of IL-7 and IL-7R expression levels in RA patients with active and inactive disease:** RA patients will be referred and informed written consent will be obtained by [name]. Blood samples will be collected from patients that have been diagnosed with RA based on ACR classification criteria. The study will include 200 donors. The total number of subjects are divided into two groups to yield a power of 95% at a type I error 5% level [determined based on the preliminary data]. In the first group, 200 donors will be treated with methotrexate, plaquenil and/or prednisone (DMARDs) that either achieve remission (DAS28<2.6) or do not achieve remission (DAS28<2.6). 50 donor will be utilized as they respond to DMARDs and achieve remission (DAS28<2.6) and 150 donors that do not respond to DMARDs will be transferred to second group. In the second group, 150 donors will be treated with methotrexate, plaquenil and/or prednisone and Cimzia® (provided to us by UCB).

In the first group of patients, blood samples will be obtained from RA patients treated with Disease modifying anti rheumatic drugs (DMARDs) such as methotrexate, plaquenil and/or prednisone that achieve remission (DAS28<2.6). The patients that achieve remission (DAS28<2.6), blood will only be taken once at the patients routine visit.

The second group will consist of RA patients that did not respond to "DMARDs". These patients will further receive (DMARDs) such as methotrexate, plaquenil and/or prednisone as well as Cimzia® (provided to us by UCB) free of charge. Cimzia® is a FDA approved drug and is a standard of care. Blood samples will be obtained from the patients treated with DMARDs including methotrexate, plaquenil, and/or prednisone and Cimzia® (provided to us by UCB) that have inactive remission (DAS28<2.6). In this group, blood samples will be collected onset of the study as well as 3 and 6 months after treatment with Cimzia at patient's visit through our collaboration with the aforementioned rheumatologists. Patients receiving intra-articular steroid injections will be excluded from the study.

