PB mononuclear cells will be isolated from RA whole blood and drawn into EDTA or CPT tubes and isolated by Histopaque gradient centrifugation. Monocytes will be isolated from RA PB mononuclear cells by negative selection (as shown in the preliminary data) and half of the monocytes will be differentiated to macrophages for 7 days. The expression levels for IL-7 and IL-7R will be determined by real-time RT-PCR and FACS analysis.

In our statistical analysis, we will first perform a stratified analysis to evaluate the differential expression levels in RA patients with active and inactive disease, controlling for the type of treatment. Data analysis will be performed in collaboration with an UIC Center for Clinical and Translational Science statistician. Specifically, we will perform the comparison of IL-7 and IL-7R expression among RA patients with active (DAS28>2.6) vs. inactive disease (DAS28<2.6) for DMARDs group (group 1). We will then perform a similar comparison for the DMARDs and Cimzia® therapy group (group 2). The stratified analysis can adjust for the potential confounding effect of treatment received and allows for the detection of the potential differential relationships between expression levels of IL-7 or IL-7R and disease status. We will also perform a pooled regression analysis in which the expression logarithm of IL-7 or IL-7R from patients is regressed on the treatment group indicator [DMARDs (group 1) versus on DMARDs plus Cimzia® therapy (group 2)] and disease status (active or inactive disease) which would demonstrate the interaction between treatment groups and disease activity. Such an analysis pools subjects from two treatment groups together and can therefore increase the sample size, and hence potentially the power of detecting the relationships between biomarkers and disease status. The RA samples will be collected over a 2 year period and the data will be analyzed in the last year of the proposal.

**Measure outcomes:** For any of the genes that demonstrate at least 2.5 fold increase (89% sensitivity calculated based on our preliminary data) in active disease compared to remission, correlation coefficient will be calculated for that gene expression level, rheumatoid factor, Cyclic Citrullinated Peptide Antibody (anti-CCP), C-Reactive Protein (CRP), DAS28 and disease duration.

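### The plan asks how IL-7/IL-7R expression relates to anti-TNF response, but no stated analysis can tell response apart from current disease activity

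*Combined protocol and SAP*

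**What the plan says.** **The question.** Section 1 (Background and Purpose) states that "we will examine whether expression of IL-7 or IL-7R in RA PB cells correlates with RA disease severity and response to" anti-TNF treatment. The same section then asks whether the two genes are markedly lower in "therapy responders compared to nonresponders". The formal wording of Aim 1 at the end of the section is narrower: it mentions only active and inactive disease by treatment.

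**The preliminary evidence.** IL-7R expression "strongly correlates with RA disease activity suggesting that IL-7R may be a predictor for disease severity", with R² = 0.56 in both monocytes and macrophages. Nothing is reported on later response.

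**The samples.** Section 2 says that "150 donors that do not respond to DMARDs will be transferred to second group", and that in this group "blood samples will be collected onset of the study as well as 3 and 6 months after treatment with Cimzia".

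**The analyses.** Section 2 lists three:
- Active versus inactive disease within group 1, followed by group 2: "We will then perform a similar comparison for the DMARDs and Cimzia® therapy group (group 2").
- A pooled regression of log expression on treatment group and "disease status (active or inactive disease) which would demonstrate the interaction between treatment groups and disease activity".
- For genes passing a 2.5-fold screen, a "correlation coefficient will be calculated for that gene expression level, rheumatoid factor", anti-CCP, CRP, DAS28 and disease duration.

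Section 10 adds paired t tests but does not say which measurements form the pair.

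**The concern.** Severity and response are two questions. Severity concerns expression and DAS28 at the same moment. Response concerns what happens to a patient after Cimzia is started. Answering it needs a time axis: either the onset value set against the later course of DAS28, or the change in expression set against the change in disease state. The sampling schedule provides that axis, but the stated analyses do not use it.

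All group 2 patients enter as DMARD nonresponders, so those inactive at month 3 or 6 are in effect the responders and those still active the nonresponders. A gene that only follows current DAS28 will differ between them. The part of the objective that concerns response would then be left unanswered, or would rest on a result that cannot be distinguished from the activity association already seen in the preliminary data.

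**Working it through.** **The plan's own figure.** The documents give no figure for the response question. The only power statement with enough inputs to check is in section 10 (paired t tests, 200 subjects, effect size 1.25, 80% power). It does not reproduce: the noncentrality is 1.25 × √200 = 17.7, so power is essentially 100%, and about 8 pairs would suffice for 80%. The present point does not depend on it.

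**Step 1: what each stated analysis uses.**

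| Analysis | Time point | Onset expression as predictor | Within-patient change | Adjusts for onset DAS28 |
|---|---|---|---|---|
| Active vs inactive, by group (section 2) | not stated | no | no | no |
| Pooled regression (section 2) | not stated | no | no | no |
| Correlations, incl. DAS28 (section 2) | not stated | not stated | no | no |
| Paired t tests (section 10) | not stated | no | possibly | no |

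A paired before/after test would use change in expression, but would not by itself bring in DAS28 or response.

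**Step 2: what the group 2 comparison shows for a pure activity marker.**
- From the documents: 150 patients; remission is DAS28 below 2.6; R² = 0.56, so r = √0.56 = 0.748.
- Assumed: onset DAS28 mean 5.0, SD 1.2, all above 2.6; change to month 6 mean −1.5, SD 1.2.
- Marker: log expression = 0.748 × standardized concurrent DAS28 + noise, with no further information on response.
- Result: the month-6 active-versus-inactive t test is significant (two-sided 5%) in over 99% of simulated studies.

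A second set of assumptions (onset SD 1, month-6 SD 1.2, 15% to 37% in remission) gives 100% at R² = 0.56, at least 99.7% at R² = 0.30, and 70% to 88% at R² = 0.10.

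**Step 3: the same marker under an onset regression.** Month-6 DAS28 is regressed on onset log expression and onset DAS28. The expression coefficient is significant in about 5% of runs under the first assumptions and 3% to 6% under the second, which is close to the nominal rate.

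**Step 4: why the adjustment is needed.** If onset expression is compared between later remitters and the others without adjustment, the second set of assumptions gives 22% to 96% significant results when onset and month-6 DAS28 correlate at 0.5, across R² from 0.10 to 0.56.

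**Step 5: is the regression feasible?** By Fisher's z with one adjustment covariate, two-sided 5% and 80% power, detectable partial r = tanh[(1.960 + 0.842)/√(n − 4)].
- n = 150: tanh(2.802/√146) = tanh(0.232) = 0.23
- n = 120 (20% loss assumed, 150 × 0.8): tanh(2.802/√116) = tanh(0.260) = 0.25
- n = 105 (30% loss assumed, 150 × 0.7): tanh(2.802/√101) = tanh(0.279) = 0.27

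**The case against.** The best counter-argument is that the documents do not promise a baseline predictor. Section 1 frames response as expression being reduced in responders, calls IL-7R a possible predictor of severity rather than of response, and words the formal aim in terms of activity only. Section 2 treats response and remission as the same thing, so active versus inactive at month 3 or 6 is a loose, unlabelled version of the responder comparison. The pooled regression, the DAS28 correlations and the paired t tests also exist, and a lagged or within-patient use of them is not ruled out.

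Much of this stands. Baseline prediction is only one reading of the response question. The other reading, change in expression by response, is not specified either, so the gap remains under both. An analysis that is merely not excluded is not a planned one.

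Two stronger readings should be resisted:
- A reader might infer that an activity marker will be reported as a response marker. The plan does not say how results will be labelled, so the documents support only that the two could not be told apart.
- A reader might infer that the plan will compare unadjusted onset expression between later responders and nonresponders, with a false-positive rate of 92% to over 99%. No such comparison is planned. That rate also depends on the assumed correlation between onset DAS28 and its change: it falls to roughly 76–79% at −0.6 and 35–37% at −0.8.

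**Conclusion.** The concern holds in a limited form. The plan poses a question about response and collects the blood needed to address it, but it specifies neither an analysis of change by response nor one of onset expression against later DAS28. The over-99% figure shows that a significant group 2 comparison would be almost certain for a marker of activity alone, so it would carry no separate evidence on response.

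That figure rests on assumed DAS28 distributions and on the preliminary R² of 0.56 carrying over to group 2. With a much weaker association (R² = 0.10) it is 70% to 88%. The near-nominal error rate of the adjusted regression held under every set of assumptions tried. DAS28 at the three draws is implied by the active/inactive classification but not scheduled in the documents.

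**What to change.** For group 2, add to the analysis description in section 2:

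1. **Definition.** Define response and its time point (month 6, and month 3 likewise), using DAS28 recorded at the onset, 3-month and 6-month draws. Section 2 also describes the Cimzia-group samples as coming from patients in remission, which conflicts with their entry as nonresponders and with the active-versus-inactive comparison; these statements must be reconciled.
2. **Change by response.** Compare change from onset in log IL-7R and log IL-7 between responders and nonresponders, adjusting for onset expression and onset DAS28, with repeat samples handled within patient. Describe the result as change that accompanies response, since a pure activity marker would also move with DAS28.
3. **Onset expression and later response.** Regress month-6 DAS28 (and month-3 DAS28) on onset log IL-7R, and separately on onset log IL-7, adjusting for onset DAS28. Report each coefficient with its 95% CI.
4. **Labelling.** Describe the active-versus-inactive comparison in group 2 as an association with disease activity. State what the paired t tests in section 10 pair.

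The cost is a few more analyses on samples already planned, and the recording of DAS28 at each draw. No extra patients or blood draws are needed. The price in interpretation is that an activity association can no longer stand in for a response association.

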#### To accomplish the proposed project we will:

**Aim 1.** Determine whether the levels of IL-7 and IL-7R are elevated in PB mononuclear cells, PB monocytes or differentiated PB macrophages of RA patients with active [disease activity score (DAS)28>2.6] and inactive disease (DAS28<2.6) treated with Disease modifying anti rheumatic drugs (DMARDs) alone and/or DMARDs plus Cimzia® (certolizumab Pegol).

#### 2. Protocol Methodology

**Detection of IL-7 and IL-7R expression levels in RA patients with active and inactive disease:** RA patients will be referred and informed written consent will be obtained by [name]. Blood samples will be collected from patients that have been diagnosed with RA based on ACR classification criteria. The study will include 200 donors. The total number of subjects are divided into two groups to yield a power of 95% at a type I error 5% level [determined based on the preliminary data]. In the first group, 200 donors will be treated with methotrexate, plaquenil and/or prednisone (DMARDs) that either achieve remission (DAS28<2.6) or do not achieve remission (DAS28<2.6). 50 donor will be utilized as they respond to DMARDs and achieve remission (DAS28<2.6) and 150 donors that do not respond to DMARDs will be transferred to second group. In the second group, 150 donors will be treated with methotrexate, plaquenil and/or prednisone and Cimzia® (provided to us by UCB).

In the first group of patients, blood samples will be obtained from RA patients treated with Disease modifying anti rheumatic drugs (DMARDs) such as methotrexate, plaquenil and/or prednisone that achieve remission (DAS28<2.6). The patients that achieve remission (DAS28<2.6), blood will only be taken once at the patients routine visit.

The second group will consist of RA patients that did not respond to "DMARDs". These patients will further receive (DMARDs) such as methotrexate, plaquenil and/or prednisone as well as Cimzia® (provided to us by UCB) free of charge. Cimzia® is a FDA approved drug and is a standard of care. Blood samples will be obtained from the patients treated with DMARDs including methotrexate, plaquenil, and/or prednisone and Cimzia® (provided to us by UCB) that have inactive remission (DAS28<2.6). In this group, blood samples will be collected onset of the study as well as 3 and 6 months after treatment with Cimzia at patient's visit through our collaboration with the aforementioned rheumatologists. Patients receiving intra-articular steroid injections will be excluded from the study.

PB mononuclear cells will be isolated from RA whole blood and drawn into EDTA or CPT tubes and isolated by Histopaque gradient centrifugation. Monocytes will be isolated from RA PB mononuclear cells by negative selection (as shown in the preliminary data) and half of the monocytes will be differentiated to macrophages for 7 days. The expression levels for IL-7 and IL-7R will be determined by real-time RT-PCR and FACS analysis.

In our statistical analysis, we will first perform a stratified analysis to evaluate the differential expression levels in RA patients with active and inactive disease, controlling for the type of treatment. Data analysis will be performed in collaboration with an UIC Center for Clinical and Translational Science statistician. Specifically, we will perform the comparison of IL-7 and IL-7R expression among RA patients with active (DAS28>2.6) vs. inactive disease (DAS28<2.6) for DMARDs group (group 1). We will then perform a similar comparison for the DMARDs and Cimzia® therapy group (group 2). The stratified analysis can adjust for the potential confounding effect of treatment received and allows for the detection of the potential differential relationships between expression levels of IL-7 or IL-7R and disease status. We will also perform a pooled regression analysis in which the expression logarithm of IL-7 or IL-7R from patients is regressed on the treatment group indicator [DMARDs (group 1) versus on DMARDs plus Cimzia® therapy (group 2)] and disease status (active or inactive disease) which would demonstrate the interaction between treatment groups and disease activity. Such an analysis pools subjects from two treatment groups together and can therefore increase the sample size, and hence potentially the power of detecting the relationships between biomarkers and disease status. The RA samples will be collected over a 2 year period and the data will be analyzed in the last year of the proposal.

**Measure outcomes:** For any of the genes that demonstrate at least 2.5 fold increase (89% sensitivity calculated based on our preliminary data) in active disease compared to remission, correlation coefficient will be calculated for that gene expression level, rheumatoid factor, Cyclic Citrullinated Peptide Antibody (anti-CCP), C-Reactive Protein (CRP), DAS28 and disease duration.

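### The single 95% power names no comparison or effect size and does not carry over to the active-versus-inactive test within group 2; the benefit claimed for pooling depends on an unstated use of the onset samples

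*Combined protocol and SAP*

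**What the plan says.** All references are to the combined protocol and SAP.

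- **Sizing (section 2, Protocol Methodology).** "The study will include 200 donors", and "The total number of subjects are divided into two groups to yield a power of 95% at a type I error 5% level". The only support given is "determined based on the preliminary data". No effect size, standard deviation, test or sidedness accompanies the 95%.
- **Groups (section 2).** The first group is introduced as all 200 donors on DMARDs, whether or not they reach remission, and is then divided: "50 donor will be utilized as they respond to DMARDs and achieve remission (DAS28<2.6) and 150 donors that do not respond to DMARDs" move on. "In the second group, 150 donors will be treated with methotrexate, plaquenil and/or prednisone and Cimzia". Section 9 gives the same 50 and 150.
- **Sampling (section 2).** For group 1, blood is described only for donors in remission, taken once. The samples at onset, 3 months and 6 months are described under group 2.
- **Analysis (section 2).** The first test is a "comparison of IL-7 and IL-7R expression among RA patients with active (DAS28>2.6) vs. inactive disease (DAS28<2.6) for DMARDs group (group 1"). Next: "We will then perform a similar comparison for the DMARDs and Cimzia® therapy group (group 2"). A pooled regression of log expression on group and disease status follows. It is also meant to show their interaction, and the plan says that it "can therefore increase the sample size, and hence potentially the power of detecting the relationships between biomarkers and disease status".
- **Section 10.** A second power statement for the same 200 subjects: 80%, paired t tests, effect size 1.25.

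No section gives the share of the 150 donors expected to reach DAS28<2.6 on Cimzia.

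**The concern.** A power figure belongs to one contrast, with its own group sizes and effect. Here one figure covers a plan with at least three tests. The group 2 test bears most directly on the stated interest in anti-TNF responders against non-responders. It uses at most 150 donors, divided by a remission rate that the plan does not give. If the 95% was computed for another split, a null result in group 2 would be read against a power never shown to apply to it.

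The pooled regression is offered as a way to gain power for disease status. If every group 1 sample comes from a donor in remission, the group indicator absorbs those donors and the gain does not occur. The group 1 test would also lack one of its two classes. A reader relying on the plan would expect three usable analyses and might find one.

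**Working it through.** **Inputs.** From section 2: 95% power, 5% type I error, 200 donors, 50 and 150. From section 10: effect size 1.25. Assumed: two-sided two-sample t test, equal variances, one sample per donor. The remission rate r in group 2 is not given, so a range is used.

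**1. The plan's own figure.** The 95% cannot be reproduced, because no effect is attached to it. With 1.25, the only effect size printed, 50 v 150 has power above 99.9%. The effect that gives 95% therefore has to be back-solved.

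The standard error factor is f = √(1/n₁ + 1/n₂). By noncentral t with 198 degrees of freedom, 95% power needs d/f = 3.62.

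- 50 v 150: f = √(1/50 + 1/150) = √0.02667 = 0.1633, so d = 3.62 × 0.1633 = 0.59.
- 100 v 100: f = √(2/100) = 0.1414, so d = 3.62 × 0.1414 = 0.51.

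**2. Group 2, active v inactive.** f(r) = √(1/(150r) + 1/(150(1−r))). This is smallest at r = 0.5, where 1/75 + 1/75 = 0.02667, exactly the value for 50 v 150. Any other split is less precise.

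| Remission in group 2 | f | Power, d = 0.59 | Power, d = 0.51 |
|---|---|---|---|
| 50% | 0.163 | 94.9% | 87.6% |
| 35% | 0.171 | 93.0% | 84.5% |
| 25% | 0.189 | 87.6% | 77.0% |
| 20% | 0.204 | 82.1% | 70.3% |
| 15% | 0.229 | 72.9% | 60.5% |
| 10% | 0.272 | 57.9% | 46.4% |

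The table is symmetric about 50%, so 65% equals 35%. The 94.9% in the first row, rather than 95.0%, reflects 148 instead of 198 degrees of freedom.

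**3. Difference detectable in group 2 with 95% power.** Scaling by f: 0.59 at 50% remission; 0.592 × 0.1886/0.1633 = 0.68 at 25%; 0.592 × 0.2287/0.1633 = 0.83 at 15%.

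**4. If the effect were 1.25.** Group 2 has 95.1% power at 9 v 141 and more with a larger minority class. But 50 v 150 then has almost 100%, so the 95% still does not describe that split. Nor does section 10's 80% fit its own inputs: a paired t test at 1.25 needs about 8 pairs for 80%, not 200 subjects.

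**5. Pooled regression, sampling text as written.** Columns: intercept, group, status. Rows: 50 group 1 donors, all inactive; 150 group 2 donors, with 37 inactive and 113 active (about 25% remission). The status standard error factor, from the diagonal of (XᵀX)⁻¹, is 0.189. Group 2 alone gives √(1/37 + 1/113) = 0.189, so the 50 donors contribute nothing to that coefficient. With the interaction added, the four-column matrix has rank 3, so the interaction cannot be estimated.

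**6. Pooled regression, onset samples counted as active DMARD-only.** Adding 150 active rows to group 1, treated as independent, lowers the factor from 0.189 to 0.124. In that case pooling does help.

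**The case against.** The strongest reply is that 50 v 150 is itself a planned test. Section 2 opens by placing all 200 donors in the first group, and section 9 repeats the division into remitters and non-remitters on DMARDs. The 150 are bled at onset, so an active sample before Cimzia can exist. On that reading 50 v 150 is the group 1 comparison, and pooling gains information as shown in step 6. This stands as a possible reading. A reader might infer that the plan never compares 50 with 150, or that pooling cannot help; the documents do not establish either. They do not settle the opposite either, since the sampling text puts the onset draw under group 2 and describes group 1 blood for remitters only.

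The second reply is that 0.59 and 0.51 are back-solved from preliminary data that the reader cannot see, and that at 1.25 group 2 is amply powered. This also stands: the size of any loss is conditional. Even at 0.59 the loss is about 2 points or less between 35% and 65% remission. The 25% row equals the plan's DMARD fraction (50/200) and is not a forecast for Cimzia. Repeated samples could add information, but the plan names no visit and no repeated-measures model.

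Neither reply rescues the 95% for group 2. Whichever 50 v 150 contrast is meant, 150 donors at the same effect can at best match it.

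**Conclusion.** The point holds in a conditional form. The 95% has no stated comparison or effect and cannot be applied to the group 2 test. At the same effect, group 2 matches a 50 v 150 calculation only if about half remit, and it cannot exceed 88% if the calculation was for 100 v 100. The loss is small near an even split and large at extreme rates (58% at 10% remission with d = 0.59). This rests on a two-sided t test, one sample per donor, equal variances and the back-solved effects.

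A reader might infer that group 2 is underpowered. The documents do not support that, because neither the true effect nor the remission rate is given.

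Separately, and without any assumed effect size: if the sampling text is followed as written, the group 1 active-versus-inactive test cannot be done, the 50 donors add nothing to the status coefficient, and the interaction cannot be estimated. This does not hold if the onset samples serve as the active DMARD-only class, which the plan does not say.

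**What to change.** **Section 2, sizing.** Keep the 95% only for the comparison and effect size it was computed for, and state both, with the test, standard deviation and sidedness. For group 2, add a short table of power for active v inactive among the 150 donors at one named visit, over a range of remission rates. Alternatively, give the difference detectable with 95% power: about 0.59 at 50% remission, 0.68 at 25% and 0.83 at 15%. Reconcile this with the 80%, paired t, 1.25 statement in section 10.

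**Section 2, analysis.** Choose one of two wordings:

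- State that the onset samples of the 150 non-responders, taken before Cimzia, are the active DMARD-only class, and model the correlation between samples from the same donor. The pooling claim can then stand.
- If they are not used that way, remove the claim that pooling increases the sample size for the disease-status coefficient, and drop the group 1 test and the interaction.

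**Cost.** Wording, one table and slightly more analysis work. The stated power becomes less favourable. No extra patients or samples are needed.

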## 9. Type and Number of Experimental Subjects

Subjects include patients over age 18, excluding pregnant women (self-reported), with an RA diagnosis, or other autoimmune disease to be used as a control. 200 donors will be treated with methotrexate, plaquenil and/or prednisone (DMARDs) that either achieve remission (DAS28<2.6) or do not achieve remission (DAS28>2.6). 50 donor will be utilized as they respond to DMARDs and achieve remission (DAS28<2.6) and 150 donors that do not respond to DMARDs will be treated with DMARDs such as methotrexate, plaquenil and/or prednisone and Cimzia provided to us by UCB. Subjects that fulfill the eligibility criteria will be identified by their physician/rheumatologist to be consented in participating in the study.

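### Cimzia response is undefined, and the only group 2 comparison that could stand in for it ignores onset DAS28 and onset expression, so a responder difference may pre-date treatment

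*Combined protocol and SAP*

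**What the plan says.** **The question.** Section 1 (Background and Purpose) asks whether the two genes are reduced in anti-TNF "therapy responders compared to nonresponders". The same section gives R² = 0.56 between IL-7R expression and disease activity, in monocytes and in macrophages.

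**The meaning of response.** Section 2 (Protocol Methodology) says "50 donor will be utilized as they respond to DMARDs and achieve remission", with remission at DAS28 below 2.6, and Section 9 repeats it. Both sentences concern the DMARD stage. Neither section, nor any other, says what counts as a response to Cimzia.

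**The analysis.** Section 2 compares active with inactive disease at DAS28 2.6 in group 1 and continues: "We will then perform a similar comparison for the DMARDs and" Cimzia group. In the pooled model, log expression is "regressed on the treatment group indicator [DMARDs (group 1) versus on DMARDs plus Cimzia® therapy (group 2)] and disease status (active or inactive disease"). Onset DAS28 and onset expression appear in neither analysis, and no visit is named for the group 2 comparison. Section 10 names a paired t test but does not connect it to responders and nonresponders.

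**The data.** Group 2 has 150 donors, with blood at onset, 3 months and 6 months. Section 9 places DMARD non-remitters above 2.6. Section 2 prints below 2.6 both for reaching and for not reaching remission, and describes group 2 samples as coming from donors below 2.6. Read literally, that leaves no active donors to compare. I follow Section 9 here; the passages must be reconciled.

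**The concern.** A fixed cut asks different things of different donors. Someone who starts just above 2.6 crosses it after a trivial fall; someone who starts high may improve a great deal and stay above it. Donors below 2.6 at follow-up will therefore tend to be those who started lower. If IL-7R tracks disease activity as the plan reports, they also started with lower IL-7R.

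Comparing follow-up expression across the cut then mixes what happened under Cimzia with what was there before it. A difference present at onset could be reported as a sign that response to anti-TNF lowers IL-7R. In the other direction, donors with large improvements who end above 2.6 are counted with the nonresponders, which blurs a true link.

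**Working it through.** The plan gives no figure of its own for this comparison. Let D0 and D6 be DAS28 at onset and month 6, and E0 and E6 log expression at the same visits.

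**Inputs from the documents:** cut-off 2.6; 150 donors in group 2; R² = 0.56 (IL-7R only). **Assumed, because the documents give none:** the distributions of D0 and of its change, and month 6 as the visit compared.

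**1. Fall needed to cross the cut** = D0 − 2.6. From 2.7 it is 0.1; from 6.0 it is 3.4. This needs no assumption.

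**2. Expression gap at onset.** The correlation is √0.56 = 0.748, so the expected onset gap in SDs of expression is 0.748 × (onset DAS28 gap ÷ SD of D0). For example, a gap of 0.87 with SD 0.8 gives 0.748 × 0.87 ÷ 0.8 = 0.81 (simulated 0.82). A gap of 0.61 with SD 0.8 gives 0.57 (simulated 0.58).

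**3. Size of the onset gap.** Two sets of assumptions were simulated.
- *Set A, 27 scenarios:* onset mean 4.0-5.0, SD 1.2, restricted to above 2.6; mean fall 1.0-2.0, SD 1.2; correlation of change with onset 0 to −0.5. Donors below 2.6 at month 6 started about 0.5-1.3 units lower. About 30-47% of the month-6 IL-7R gap was present at onset.
- *Set B, 16 settings:* onset mean 4.5 or 5.5, SD 0.8 or 1.2; SD of change 1.0 or 1.5, independent of onset; 20% or 35% reaching below 2.6. Onset gap 0.6-1.5 units; onset share of the end-score gap 21-58%; expression gap at onset 0.56-0.98 SD.

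**4. False positives when treatment leaves the marker unchanged** (n = 150, two-sided 5%). Onset mean 5, change independent of onset, 2,000 trials per row:

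| SD of D0 | SD of change | Share below 2.6 | Unadjusted | Adjusted for D0 |
|---|---|---|---|---|
| 0.8 | 1.5 | 20% | 86.9% | 5.4% |
| 0.8 | 1.5 | 35% | 93.2% | 6.1% |
| 1.0 | 1.2 | 30% | 99.7% | 4.6% |
| 1.2 | 1.0 | 20% | 99.9% | 4.7% |
| 1.2 | 1.0 | 35% | 100% | 6.0% |

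Across Set A, which allows higher starters to fall further, the unadjusted figure was about 67-100%. With D0 and E0 as covariates it was about 3-8%, around the nominal 5%.

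**5. Change in expression instead of level.** Comparing E6 − E0 across the same cut in the same null situation gave 2.5-6.7% false positives, about nominal.

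**6. Dilution by the cut** (Set A, expression tracking DAS28). Of donors falling by at least 1.5, 21-76% were labelled nonresponders. The standardised contrast in expression change was 0.71-1.16, against 1.50-1.67 when the same number of donors were labelled by size of fall.

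**7. Fall or end state as regressor.** With D0 in the model, b1(D0 − D6) + b2·D0 = −b1·D6 + (b1 + b2)·D0. The coefficient on the fall is that on D6 with its sign reversed, and the p-value is the same.

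**The case against.** **The DMARD sentence does not define Cimzia response.** A reader might infer that the plan defines a Cimzia responder as a donor in remission. It does not: that reading is only implied by reusing the 2.6 cut. This objection stands. The documented gap is that a response question is posed with neither a definition nor an analysis of its own.

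**Comparing current disease state is legitimate.** Aim 1 as listed asks about active and inactive disease. For that, current DAS28 is the right grouping and onset severity need not be removed. This also stands. But Section 1 attaches response to anti-TNF treatment to the same aim, and a current-state comparison cannot answer that part.

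**Is the label confounded whatever is compared?** A reader might infer that it spoils a comparison of change in expression too. Step 5 does not support this: in the null situation tested, false positives were near nominal. What remains is dilution, and at n = 150 its cost in power is modest. Power for the change comparison under the 2.6 label was 89-100%, and at least 96% in 26 of 27 scenarios.

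**Is the end state itself at fault?** Step 7 shows not. The faults are the missing onset adjustment and the dichotomy.

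**The sizes rest on assumptions.** True. In a further check of the less favourable case (correlation −0.5, onset mean 5, SD 1, 20-35% below 2.6), unadjusted false positives were 60-68%, and 4-5% after adjustment. The magnitude moves; the direction does not.

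**Conclusion.** The concern holds for the group 2 response question and no further. A fixed cut, varying starting scores, a marker tied to severity and no onset term in any model together mean that the planned comparison cannot separate response to Cimzia from onset severity. That direction follows from the documents.

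The size does not. If the assumed distributions are roughly right, about a third to a half of the month-6 IL-7R gap would have been there at onset. A marker untouched by treatment would be declared different in at least about two-thirds of trials in most scenarios. Onset adjustment brings this back to about 5%. The R² of 0.56 is reported for IL-7R only, so nothing is claimed about the size for IL-7. Nor do the documents support calling the active/inactive comparison invalid for its own purpose.

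This should be changed before analysis: the correction is cheap and can reverse the conclusion on the response question.

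**What to change.** In the statistical part of Section 2, for the group 2 response question only:

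- State that response to Cimzia is analysed as the fall in DAS28 from onset to month 6, kept continuous.
- Fit E6 = b0 + b1(D0 − D6) + b2·D0 + b3·E0 for log IL-7 and log IL-7R, and test b1.
- If the remission split is kept for this question, report it as secondary, with D0 and E0 as covariates.
- Leave the active/inactive comparison for Aim 1 as it is, and do not describe its group 2 result as a comparison of responders with nonresponders.
- Reconcile the DAS28 limits for group 2 between Sections 2 and 9.

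This concerns the analysis only, not who is treated. The cost is wording: onset and month-6 blood is already planned. The plan should confirm that DAS28 is recorded at both visits. The downside is that the simple responder/nonresponder table becomes secondary.
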